8.2.1. Primary Outcome

The primary outcome will be the incidence of malaria, defined as the number of incident episodes per time at risk. Incident cases will include all treatments for malaria not proceeded by another treatment in the previous 14 days. Time at risk will begin at birth and will end when study participants reaches 12 months of age or early study termination (if prior to 12 months of age).

8.2.2. Secondary Outcomes

Secondary outcomes are summarized in Table 4 below.

···· ··· ···	
Secondary outcome	Definition
Incidence of complicated malaria	Any treatment for malaria meeting criteria for
	severe malaria or danger sings
Incidence of hospital admissions	Admission to the pediatric ward for any cause
Infant mortality rate	Any deaths occurring after birth
Prevalence of anemia	Proportion of routine hemoglobin measurements
	< 10 g/dL & < 8 g/dL
Prevalence of asymptomatic	Proportion of routine samples (by microscopy or
parasitemia	LAMP) positive for asexual parasites.

Table 4. Secondary outcomes

8.2.3. Analyses

A modified intention-to-treat approach to all analyses will be used, including all live infants born and including all follow-up time until the study participants reach 12 months of age or early study termination regardless of whether the infant's mother received her assigned IPTp regimen.

Primary analysis. We will compare the incidence of malaria using Poisson or negative binomial regression models as described in section 8.1.3. If necessary, multivariate analyses will be performed to adjust for potential confounders and effect modifiers.

Secondary analyses. We will compare the incidence of complicated malaria and hospitalizations using Poisson or negative binomial regression models as described in section 8.1.3. We will compare the prevalence of anemia and asymptomatic parasitemia using generalized estimating equations with adjustments for repeated measures in the same study participant. If necessary, multivariate analyses will be performed to adjust for potential confounders and effect modifiers.

8.3. Hypothesis 3

We will test the hypotheses that a metabolic dating algorithm developed in a western setting can also be used for gestational dating in Uganda. We will also test the hypothesis that metabolic markers – especially those related to glucose metabolism can be used to identify newborns at more or less risk for death and serious morbidities.

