3. STUDY DESIGN

This will be a double-blinded randomized controlled phase III trial of 782 HIV uninfected pregnant women and the children born to them. HIV uninfected women at 12-20 weeks gestation will be randomized in equal proportions to one of two IPTp treatment arms: 1) monthly SP, or 2) monthly DP. Both interventions arms will have either SP or DP placebo to ensure adequate blinding is achieved in the study as outlined in appendix D. Follow-up for the pregnant women will end approximately 6 weeks after giving birth. All children born to mothers enrolled in the study will be followed from birth until they reach 12 months of age.

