4.4. Study Enrollment Procedures and Baseline Evaluation

Informed consent will be obtained from women who pass initial screening. Study physicians will conduct the informed consent discussion in the study clinic. Informed consent will include both participation of the pregnant woman and her unborn child (or children in the case of nonsingleton pregnancies). Informed consent will be conducted in the appropriate language and a translator will be used if necessary. The study will be described and consent obtained in one of 4 languages (Samia, Swahili, Luganda, or English). The consent forms will be translated into each language and back-translated into English to check for any loss or change of meaning. Following the informed consent discussion, pregnant women will be asked by the study physicians to sign a written consent form approved by the UCSF Committee for Human Research (UCSF CHR), Makerere University School of Biomedical Sciences - Research and Ethics Committee (SBS-REC), and the Uganda National Council for Science and Technology (UNCST) for their own participation in the research study and a second approved consent form for the future use of biological specimens obtained during the course of the study. If the pregnant woman is unable to read or write, her fingerprint will substitute for a signature, and a signature from an impartial witness to the informed consent procedures will be obtained. The father will also be asked to provide written consent or a fingerprint to allow participation of the unborn child. If a father is unknown or unavailable, the woman will document in accordance with UNCST guidance and participation will continue for both the woman and infant. If the biological father refuses consent for the child's participation, the child will not be enrolled but the mother may still be enrolled.

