5. STUDY TREATMENT

5.1. Treatment Group Assignments

There will be 2 treatment arms for the woman during pregnancy; monthly SP or monthly DP. We will use a 1:1 randomization scheme targeting 391 pregnant women in each treatment arm. A randomization list will be computer generated by a member of the project who will not be directly involved in the conduct of the study. The randomization list will include consecutive treatment numbers with corresponding random treatment assignments. Randomized codes will correspond to the 2 treatment arms using permuted variable sized blocks of 4 and 8. Sealed copies of the original randomization list and documentation of the procedure used to generate the lists will be stored in the project administrative offices in San Francisco and Kampala. Prior to the onset of the study, a set of sequentially numbered, opaque, sealed envelopes will be prepared. Each envelope will be marked on the outside with the treatment allocation number. The inside of the envelope will contain a piece of paper with the treatment allocation number and treatment group assignment along with a piece of carbon paper.

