8. STATISTICAL CONSIDERATIONS

8.1. Hypothesis 1

We will test the hypothesis that pregnant women who receive IPTp with monthly DP will have a lower risk of a composite adverse birth outcome defined as LBW, preterm delivery or SGA compared to those who receive monthly SP. Secondary outcomes will include incidence of malaria and adverse events during pregnancy, risk of asymptomatic parasitemia and anemia during pregnancy, and measures of placental malaria at the time of delivery. For women with non-singleton birth (i.e. twins), dichotomous delivery outcomes at the level of the individual child/placenta will be based on whether the outcome was present in either child/placenta.

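### Section 8.2.3 sets no mother-level clustering for twins, so standard errors for the modelled infant outcomes are slightly too small if twins' outcomes are positively correlated

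*Combined protocol and SAP*

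**What the plan says.** - **Randomised unit.** Section 5.1: "We will use a 1:1 randomization scheme targeting 391 pregnant women in each treatment arm".
- **Twins are in the study.** Section 4.4 takes consent for the unborn child, "or children in the case of nonsingleton pregnancies". Section 3: "All children born to mothers enrolled in the study will be followed from birth until they reach 12 months of age". The exclusion criteria in section 4.2 do not rule out multiple pregnancy.
- **Hypothesis 2 analysis set.** Section 8.2.3 uses a modified intention-to-treat set "including all live infants born and including all follow-up time".
- **Primary model.** Section 8.2.3: "We will compare the incidence of malaria using Poisson or negative binomial regression models as described in section 8.1.3". The same model families serve complicated malaria and hospitalisations. The only variance adjustment that section 8.1.3 offers for them is for overdispersion.
- **Prevalence outcomes.** Anaemia and asymptomatic parasitaemia are compared using "generalized estimating equations with adjustments for repeated measures in the same study participant".
- **The one twin rule.** Section 8.1, under Hypothesis 1: "For women with non-singleton birth (i.e. twins), dichotomous delivery outcomes at the level of the individual child/placenta will be based on" whether the outcome occurred in either child or placenta.

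**The concern.** Both twins always carry their mother's allocation. They also share her pregnancy, which is the exposure that Hypothesis 2 is about, and normally the household. Two records from one randomised woman therefore hold less information than two records from different women if the twins' outcomes move together. A model that takes infants as independent then reports intervals that are too narrow and a type I error above the nominal level. This bears on the primary test of Hypothesis 2 and on four of its secondary outcomes.

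Section 8.1 recognises the issue for delivery outcomes and resolves it with one result per woman. That rule is limited to dichotomous delivery outcomes. It does not reach episode counts or repeated measurements over the first year of life.

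**Working it through.** **1. The plan's own figures.** The documents state no twin rate, within-pair correlation or design effect, so there is no stated twin adjustment to reproduce. The nearest figures are in section 8.4.

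- *Sample size.* With 30.4% vs 21.4%, two-sided 5% and 80% power, the two-proportion formula gives 371 women per arm, 742 in total. Then 742/0.95 = 781.05, rounded up to 782. This agrees with the plan.
- *Detectable difference for Hypothesis 2 (18-23% at 3-5 episodes per person-year).* Plain Poisson with 371 infants per arm and 0.95-1.0 years of follow-up gives 9.0-11.8%. A variance factor of about 4.1 matches both ends (18% at 5 episodes, 23% at 3). The figure therefore fits an overdispersion allowance that the plan does not state, and cannot be confirmed. That is a separate matter; it is used here only as the reference for step 5.

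**2. Formula.** Let t be the share of pregnancies that are twin and ρ the within-pair correlation. Since both twins are always in the same arm,

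DEFF = 1 + ρ × (Σm²/Σm − 1) = 1 + ρ × 2t/(1 + t).

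The correct standard error is √DEFF times the infant-level one. The actual level of a nominal 5% test is 2 × [1 − Φ(1.96/√DEFF)].

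**3. Results.** Both t and ρ are assumptions.

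| t | ρ | 2t/(1+t) | DEFF | SE understated by | Actual level |
|---|---|---|---|---|---|
| 2% | 0.3 | 0.0392 | 1.012 | 0.6% | 5.1% |
| 2% | 0.5 | 0.0392 | 1.020 | 1.0% | 5.2% |
| 3% | 0.5 | 0.0583 | 1.029 | 1.45% | 5.3% |
| 4% | 0.7 | 0.0769 | 1.054 | 2.7% | 5.6% |
| 5% | 1.0 | 0.0952 | 1.095 | 4.7% | 6.1% |

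The last row is an outer limit, not an expectation.

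**4. Simulation check (20,000 trials per setting; Monte Carlo error of a 5% level = √(0.05 × 0.95/20,000) ≈ 0.0015).**

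| Twin pregnancies | Pairs sharing frailty | SE ratio, mother/infant level | Level, infant-level SE | Level, mother-level SE |
|---|---|---|---|---|
| none | – | 1.000 | 0.052 | 0.052 |
| 2% | half | 1.007 | 0.051 | 0.050 |
| 3% | half | 1.011 | 0.056 | 0.054 |
| 5% | all | 1.034 | 0.061 | 0.053 |

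Solving the formula backwards, ρ = (ratio² − 1)/[2t/(1+t)] gives 0.36, 0.36 and 0.73. Even with fully shared frailty, the correlation between counts stays below 1, because Poisson noise dilutes it. Under a shared-frailty negative binomial model the ceiling is kμ/(1 + kμ). At the dispersions implied by section 8.4 (k = 0.70 at 5 episodes, 1.22 at 3, with 0.975 years of follow-up) this is 3.43/4.43 = 0.77 and 3.57/4.57 = 0.78. As μ falls the ceiling falls towards zero, so complicated malaria and admissions probably lie at or below the low end of the range.

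**5. Effect on the Hypothesis 2 power statement.** At 2% twins and ρ = 0.5, with the number of infants fixed, the detectable difference moves from 18.1% to 18.2% (5 episodes) and from 23.0% to 23.2% (3 episodes). Twins also add infants: 371 × 1.02 = 378.4 per arm, and 378.4/1.0196 = 371.1 effective. The gain and loss cancel at about ρ = 0.5.

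**6. GEE outcomes.** The working correlation covers repeated samples from one infant. The formula in step 2 applies approximately, with ρ read as the correlation between the two twins' summed residuals. No separate value was derived for anaemia or parasitaemia, so the range in step 3 is only a guide for them.

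**The case against.** **The plan nowhere says that twins are independent.** This is true. Section 8.2.3 names model families and is silent on siblings, and a careful analyst might cluster on the mother anyway. A reader might infer a deliberate choice to ignore pairing; the documents do not show one. But followed as written, the count models have no cluster term, and the GEE corrects only within a participant. In 8.2.3 that participant is the infant, since follow-up is defined as running to 12 months of age.

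**Section 8.1.3 allows variances to be adjusted to give valid inference.** That sentence concerns overdispersion. An overdispersion factor enlarges the variance of each infant's count; it does not add the covariance between two infants of one mother.

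**The size rests on assumptions.** This stands for both the twin rate and the correlation. A positive correlation is well founded, since the pregnancy and normally the home are shared, but it is not documented.

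**Clustering does not bring the simulated level exactly to 5%.** At 3% twins it moved from 0.056 to 0.054. The setting without twins gave 0.052 by either method, so the remainder is within reach of baseline behaviour and Monte Carlo error.

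**All infant secondary outcomes are affected.** A reader might infer this, but it goes too far. Infant mortality is listed in Table 4, yet 8.2.3 names no test or model for it, so there is no standard error to call too small. The gap there is a missing method.

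**Conclusion.** The omission is clear from the text; its size is small and conditional. For infant malaria, complicated malaria, hospitalisations, anaemia and asymptomatic parasitaemia, the stated methods give slightly understated standard errors if twins' outcomes are positively correlated. With 2-4% twin pregnancies and a correlation of 0.3-0.7, both assumed, the understatement is about 0.6-2.7% and the actual level of a 5% test about 5.1-5.6%. Only a borderline result could change.

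Two stronger conclusions do not follow. The 18-23% detectable difference in section 8.4 is not materially altered by twins. Hypothesis 1, which set the sample size, keeps one result per woman for its primary outcome under section 8.1. This is a worthwhile refinement rather than a threat to the trial's conclusions.

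**What to change.** In section 8.2.3, state that:

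- the Poisson and negative binomial models for malaria, complicated malaria and hospitalisations use robust (sandwich) standard errors with the mother as cluster;
- the GEE for anaemia and asymptomatic parasitaemia uses the mother as cluster, with repeated measures nested within infant.

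If 8.2.3 is being edited, a method for infant mortality could be named at the same time, with the same clustering.

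The cost is a sentence in the plan and an option in standard software. It needs no new data or extra participants, and the treatment comparison stays the same. Intervals become up to about 3% wider under the assumed range. Fixing the rule in advance also removes a later choice between ignoring pairs, dropping one twin and clustering.

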8.3.1. Primary Outcomes

The primary outcomes will be preterm birth (< 37 completed weeks gestation) as determined by ultrasound dating and an existing gestational dating by metabolic profile algorithm. With respect to newborn outcomes, primary outcomes will be survival to 24 hours, 48 hours, 7 days, 30 days, and to the first year of life as well as diagnoses of any major morbidity including necrotizing enterocolitis, respiratory distress syndrome, and retinopathy of prematurity or blindness.

8.3.2. Secondary Outcomes

Secondary outcomes of interest include SGA birth outcome and the capacity of metabolic markers to correctly date a pregnancy in the context of intra-uterine growth restriction. Also, we will evaluate whether metabolic associations with survival and morbidity differ by SGA status.

8.3.3. Analyses

Analyses will focus on model validation for both the gestational dating and neonatal survival and morbidity using predictive models that have been or will be built using a population of more than 720,000 newborns in California using linear discriminate analyses.

Primary analysis. We will compare categorization of a newborn as preterm or not and specific week of gestation using the metabolic algorithm versus ultrasound dating. We will also compare predicted survival and diagnoses based on metabolic prediction versus true events and diagnoses. Performance will be measured using sensitivity, specificity, positive predictive value, negative predictive value, positive likelihood ratio, and negative likelihood ratio.

Secondary analyses. We will compare performance statistics in newborns with and without SGA (sensitivity, specificity, positive predictive value, negative predictive value, positive likelihood ratio, and negative likelihood ratio).

8.4. Sample size and power

The number of pregnant women enrolled and the number of study participants reaching the various endpoints will determine the samples sizes for each of the primary outcomes of our study aims. The primary determinant of our target sample size was based on testing hypotheses 1. Based on our previous studies, we estimate that 95% of pregnant women enrolled will reach the primary study endpoint and we will lose 5% of follow-up time per year in the infants. The study will be powered to detect a significant difference in the risk of our composite adverse birth outcome between the 2 study arms. Considering pregnancies resulting in either low birth weight (< 2500 gm), small for gestational age, or premature delivery (< 37 weeks) in our previous study, the risk was 21.4% in the monthly DP arm compared to 30.4% in the 3 dose SP arm. Assuming the same risks, we would need to enroll 782 women (assuming 5% loss to follow-up during pregnancy) to have 80% power (2-side alpha = 0.05) to detect a 30% or greater reduction in the relative risk of our composite birth outcome. For hypothesis 2, we will have 80% power (2-side alpha = 0.05) to detect an 18-23% relative difference in the incidence of malaria between 0-12 months of age among children born to mothers randomized to the 2 IPTp arms assuming an incidence of malaria ranging from 3-5 episodes PPY among children born to mothers randomized to receive IPTp with monthly SP. Hypothesis 3 relies on the collected study data and samples to validate existing gestational dating, survival, and morbidity algorithms and as such, no limitations in statistical power are anticipated.

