Using metabolic profiles in the newborns for gestational age dating and evaluation of outcomes. As is noted in the background section, our group is experienced in examining the relationship between metabolic profiles at birth, gestational age, and newborn outcomes. Specifically, we recently evaluated whether metabolic markers in newborns could be used to develop a population-level metabolic gestational dating algorithm that is robust despite intrauterine-growth restriction and could be used when fetal ultrasound dating is not available. We focused specifically on the ability of these markers to differentiate preterm births (<37 weeks) from term births and to assign a specific gestational age in the preterm birth group. In a cohort of 729,503 singleton newborns we used multivariate backward stepwise regression to test for associations and linear discriminate analyses to create a linear function for preterm birth and to assign a specific week of gestation. These efforts resulted in a finding that when considered with birth weight and timing of test by hours after birth at blood draw, 35 of the 51 metabolic markers evaluated were able to sort preterm and term births accurately with sensitivities and specificities of 95% or more in both the training and testing subsets.

correct assignment of week +/-2 weeks in 89.8% of all newborns in the training and 91.7% of those in the testing subsets.⁴⁵

Our group is also uniquely prepared to investigate the relationships between metabolic markers and newborn outcomes given extensive work with similar data and specimens. Of particular note is work from our group that has shown that preterm neonates are metabolically different than their term peers.⁴²⁻⁴⁴ Also important are our findings demonstrating differences in glucose-related markers in preterm birth neonates within the first few days of life that go on to develop complications of prematurity including respiratory distress syndrome and necrotizing enterocolitis. Recently we found that that acylcarnitine patterns within the first few days of life can help identify more than 80% of preterm neonates that develop necrotizing enterocolitis.

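### Section 8.4's claim of no power limitation for Hypothesis 3 does not follow from validating existing algorithms, and is unsupported for the sensitivity of uncommon death and morbidity outcomes

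*Combined protocol and SAP*

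**What the plan says.** Section 8.4 opens with the right principle: "the number of study participants reaching the various endpoints will determine the samples sizes for each of the primary outcomes". It then sizes the trial on Hypothesis 1, where in the previous study "the risk was 21.4% in the monthly DP arm compared to 30.4% in the 3 dose SP arm", and arrives at 782 women with 80% power and 5% loss. Hypothesis 2 receives a detectable difference of 18–23%. Hypothesis 3 receives no figure. The section says that it validates existing dating, survival and morbidity algorithms on the study's data and samples, "and as such, no limitations in statistical power are anticipated".

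Section 8.3.1 lists the Hypothesis 3 primary outcomes. Besides preterm birth, the "primary outcomes will be survival to 24 hours, 48 hours, 7 days, 30 days, and to the first year of life", together with major morbidity, for which it names necrotizing enterocolitis, respiratory distress syndrome, and retinopathy of prematurity or blindness. Section 8.3.3 says how the predictions are judged: "Performance will be measured using sensitivity, specificity, positive predictive value, negative predictive value, positive likelihood ratio, and negative likelihood ratio". It also describes validation "using predictive models that have been or will be built using a population of more than 720,000 newborns in California".

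The documents give no expected rate for death or for any of these morbidities. For Hypothesis 3 they state no precision target and no requirement to report confidence intervals.

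**The concern.** The only reason offered for having no power limitation is that the algorithms already exist. The size of the development population limits the error in the model. It does not limit the error in an estimate of how well the model performs in Busia. Sensitivity is a proportion whose denominator is the number of affected newborns in this cohort, and the likelihood ratios inherit its uncertainty. The closing sentence on Hypothesis 3 therefore sets aside the principle with which section 8.4 begins. The premise is also only partly met, since section 8.3.3 allows that some models are still to be built.

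At stake is how the Hypothesis 3 results are read. A sensitivity based on a handful of deaths or diagnoses could be taken as adequately powered validation because the plan told the reader to expect no limitation. The secondary analysis by small-for-gestational-age status divides the same events further.

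**Working it through.** **The plan's own figure.** Two proportions, 0.304 and 0.214, pooled variance, no continuity correction, 80% power, two-sided 0.05: 371 per arm. Then 742 / 0.95 = 781.05, rounded up to 782. The stated sample size reproduces and is not in dispute. Hypothesis 3 has no stated figure to reproduce.

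**Inputs**
- Newborns: 782 × 0.95 = 742.9, about 743, taking one newborn per woman (section 8.4).
- Event rates: assumed, 0.5% to 10%, because the documents give none.
- Observed sensitivity: assumed, as near 80% as whole numbers allow. The only related figure is background in section 1.2, that "acylcarnitine patterns within the first few days of life can help identify more than 80% of preterm neonates that develop necrotizing enterocolitis".

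**Method.** Events = 743 × rate, rounded. True positives = 0.80 × events, rounded. The exact (Clopper-Pearson) 95% limits for x of n are the 0.025 quantile of Beta(x, n − x + 1) and the 0.975 quantile of Beta(x + 1, n − x).

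| Assumed rate | 743 × rate | Observed sensitivity | Exact 95% CI | Width (points) |
|---|---|---|---|---|
| 10% | 74.3 | 59/74 (80%) | 68.8–88.2% | 19.4 |
| 5% | 37.2 | 30/37 (81%) | 64.8–92.0% | 27.2 |
| 2% | 14.9 | 12/15 (80%) | 51.9–95.7% | 43.8 |
| 1% | 7.4 | 6/7 (86%) | 42.1–99.6% | 57.5 |
| 0.5% | 3.7 | 3/4 (75%) | 19.4–99.4% | 80.0 |

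The width is not an artefact of the exact method: the Wilson interval for 12/15 is 54.8–93.0%.

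**Survival time points.** The denominator should be live infants under follow-up. Table 9 shows 3 stillbirths, and section 1.2 gives 300 women randomized in that study, so 1%: 743 × 0.99 = 736 live newborns. Section 8.4 adds that "we will lose 5% of follow-up time per year in the infants". Treating this roughly as 5% fewer infants at one year, 736 × 0.95 = 699. At an assumed 5% event rate that gives 28/35, 63.1–91.6%. At 2% it gives 11/14, 49.2–95.3%.

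**Where precision is adequate or better**
- Specificity rests on the unaffected newborns. At a 2% event rate there are 743 − 15 = 728. At an assumed 95% specificity, 692/728 has an exact 95% CI of 93.2–96.5%.
- Preterm classification at an assumed sensitivity near 95%: 70/74 gives 86.7–98.5% at an assumed 10% prevalence, and 35/37 gives 81.8–99.3% at 5%.
- Week-of-gestation assignment was not assessed.

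**The case against.** **The rates are not the protocol's.** This is true, and it sets the limit of the point. Every row of the table needs an assumed event rate and an assumed sensitivity. A reader might infer that the sentence in section 8.4 is shown to be false, or that Hypothesis 3 is underpowered. The documents do not support that: with no event rates they show only that the assurance has no basis. At a 10% rate the interval is under 20 points wide, which many would accept.

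**Morbidity may be one combined outcome.** Section 8.3.1 can be read as any major morbidity, with the named conditions as examples. On that reading the 5% and 10% rows may be the relevant ones and the imprecision is moderate. The wording does not settle which reading is meant.

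**Section 8.4 speaks of power, not precision.** Section 8.3.3 sets no null value or threshold, so there is no test whose power could be computed. This stands as a matter of terminology. It does not rescue the assurance, because planned precision is the usual counterpart of power for an estimation aim, and the plan states neither.

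**The benchmark for necrotizing enterocolitis.** A reader might infer that the trial must confirm the figure of more than 80% in section 1.2, among preterm newborns only. No such comparison is planned. Section 8.3.3 compares predictions with actual events and diagnoses, and the benchmark is background. It serves here only as the source of the assumed 80%.

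**Hypothesis 3 did not drive the sample size.** This is correct, and the randomized comparisons under Hypotheses 1 and 2 are unaffected. It would justify saying that precision is limited for rare outcomes. It does not justify an unqualified statement that covers survival and morbidity by name.

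**Conclusion.** The statement in section 8.4 does not follow from its stated reason, and this conclusion needs no assumed rate. For uncommon death and morbidity outcomes it is unsupported. With about 743 newborns and an observed sensitivity near 80%, the exact 95% interval is about 27 points wide at a 5% event rate, 44 at 2%, 58 at 1% and 80 at 0.5%. These widths rest on the assumed rates and sensitivity, and the concern weakens at about 10%.

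The point does not extend to every measure: specificity would be estimated precisely and preterm classification is less affected. It does not call the sample size of 782 into question.

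**What to change.** Replace the Hypothesis 3 sentence in section 8.4 with text such as:

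> Precision for Hypothesis 3 depends on the number of newborns with each outcome. The rates and the sensitivity near 80% used here are planning assumptions. With about 743 newborns, outcomes affecting 10%, 5%, 2%, 1% and 0.5% would give about 74, 37, 15, 7 and 4 events. Observed sensitivities of 59/74, 30/37, 12/15, 6/7 and 3/4 would have exact 95% CIs of 69–88%, 65–92%, 52–96%, 42–99.6% and 19–99%. For preterm classification, 70/74 (assumed 10% prevalence) would have an exact 95% CI of 87–99%. Estimates of sensitivity for uncommon death and morbidity outcomes will therefore be imprecise; specificity will be estimated precisely.

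For each survival time point, use live newborns under follow-up as the denominator. State whether major morbidity is one combined outcome or several, so that the reader knows which rows apply.

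In section 8.3.3 add:

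> Every performance measure will be reported with its number of events and 95% CI (exact for proportions).

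The cost is a few sentences. Sample size, outcomes and procedures stay as they are. The one drawback for the sponsor is a less favourable statement about Hypothesis 3.
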